### **6.3 Methods for Unblinding**

All efforts should be made to keep participants blinded to treatment assignment. However, participants may be unblinded to treatment assignment upon request from the investigator and agreement by the Sponsor if knowledge of treatment assignment will impact future treatments or clinical care of the participant. Unblinding by the investigator independently of the Sponsor also may occur if an AE or toxicity necessitates identification of the medication for the welfare of the participant. Please refer to the Suvoda Interactive Web Response System Manual for the unblinding process and contact information.

## **7 STUDY TREATMENT**

Study drug is defined as mavacamten (MYK-461) or placebo.

All randomized study participants will receive either mavacamten or placebo in a double-blinded manner.

## 7.1 Mavacamten and Matching Placebo, Administration, and Schedule

Mavacamten capsules and matching placebo have the same appearance. The study drug presentation is size 2, blue opaque capsules printed with a yellow band on the body and black band on the cap. Each capsule contains white to off-white powder. The active capsules are supplied in 4 strengths: 2.5 mg, 5 mg, 10 mg, and 15 mg.

Mavacamten active and placebo capsules have been manufactured according to current Good Manufacturing Practice (cGMP) regulations. They will be supplied in high-density polyethylene bottles with induction seals and child-resistant caps at 30 count per bottle. All study drug will be labeled according to applicable local regulatory guidelines.

The mavacamten active and placebo capsules must be stored at 2°C to 25°C (36°F to 77°F) in the packaging supplied by MyoKardia. Study medication at the investigational site will be stored in a secure area with access limited to authorized study personnel.

Study drug will be supplied to participants in 30-count high-density polyethylene bottles that are appropriately labeled. Refer to [Table 1](#) for the complete schedule of study drug administration. Participants will take study drug as directed by the study investigator. The participants will be instructed to store the study drug capsules and bottles in a cool, dry place. Study drug should be taken with approximately 8 ounces (48 tablespoons or ~235 mL) of water.

## 7.2 Treatment Compliance

Compliance with study drug will be monitored by capsule count at all study visits. Refer to the Pharmacy Manual for details.

Participants should be instructed to take the study drug at approximately the same time every day ( $\pm 8$  hours). If the dosing window is missed, the participant should not take study drug that day. Participants should never receive 2 doses of study drug within an 8-hour period.

On study visit days, participants should wait to take study drug until after they reach the clinic and have a PK blood sample taken as indicated in the schedule of study procedures ([Table 1](#)). Any concomitant medication may be administered prior to all exercise testing.

## 7.3 Dose Adjustments

### 7.3.1 *Blinded Dose Adjustments During Double-blind Treatment Period*

#### 7.3.1.1 Dose Titration Period (Day 1 to Week 14)

The double-blind treatment period will include a two-step dose titration scheme at Week 8 and Week 14 designed to achieve safe and effective dosing for each participant based on their own PK/PD response parameters ([Figure 1](#) and [Table 3](#)).

In this study, the starting dose of study drug is mavacamten 5 mg or matching placebo QD, and each participant will receive this dose of study drug from Day 1 through Week 8 unless a

PK/PD criterion is met at Week 4, in which case the dose will be reduced at Week 6 ([Table 3](#)).

At Weeks 8 and 14, participants will undergo dose adjustment (dose increase, dose decrease, or dose unchanged) based on their results from PK/PD assessments at Week 6 and Week 12, respectively ([Table 3](#)). Note that Table 3 is provided for IXRS programming. Sites and investigators will not be actively adjusting doses. All dose adjustments will occur in a double-blind manner via IXRS, and all participants, whether receiving mavacamten or matching placebo, will undergo assessments that could lead to a blinded dose adjustment. However, note that participants who are on placebo will remain on placebo (in blinded fashion) unless the participant has a temporary discontinuation as described in [Section 7.3.2](#) or a permanent treatment discontinuation as described in [Section 7.3.3](#) and [Section 10.1.3](#).

For added safety, a Week 8 blood sample will be drawn to determine trough plasma PK. If PK is greater than 700 and less than 1000 ng/mL, then an unscheduled visit will be arranged 2 weeks later to reduce dose (see [Table 3](#)). Dose reduction will occur via IXRS. To avoid potential bias the IXRS will randomly select a participant from the placebo arm to undergo an unscheduled follow-up visit (see also [Section 6.2](#)).

If the mavacamten dose is decreased at any time during the study, then the participant will continue on the reduced dose to the EOT (Week 30) unless safety concerns or intolerance arise requiring further dose reduction or dose discontinuation.

[figure not shown]
Based on PK modeling informed by prior mavacamten clinical studies, and depending on the demographics of enrolled patients, it is estimated that the following percentages of participants will reach the target steady-state concentrations for the following doses: 2.5 mg (< 1%), 5 mg (5–20%), 10 mg (40–50%), and 15 mg (30–55%).

If the PK/PD criteria for down-titration are met, then dose reduction will be implemented as follows:

The diagram illustrates a hierarchical data structure. At the top, there are several horizontal bars of varying lengths. A blue arrow points downwards, indicating a process or flow. Below the arrow, there are two groups of horizontal bars. The first group contains four bars of increasing length. The second group contains four bars of increasing length, with the first bar being the longest. The bars are black on a white background.

### 7.3.1.2 Dosing Period (Week 14 to Week 30)

After the second dose titration at Week 14, there are no further up-titrations; the intent is for dose to remain unchanged unless for safety or other reasons for premature discontinuation (see Section 7.3.2 and [Section 10.1](#)). After Week 14, participants will return to the clinical site for monitoring at scheduled 4-week intervals (Weeks 18, 22, 26, and 30 [ $\pm 7$  days]). At each visit, AEs, concomitant medications, and symptoms will be assessed, and ECG, plasma PK, and TTE will be performed for ongoing safety monitoring. Compliance with study drug will also be monitored by capsule count at each visit. If PK/PD criteria are met, then an unscheduled visit 2 weeks later will be required to reduce dose as shown in Table 4.

### 7.3.2 *Blinded Dose Adjustment Leading to Temporary Discontinuation*

In addition to the blinded dose adjustments described above (which are not preceded by dose discontinuation), at any time (T) during the treatment period, dosing may be temporarily discontinued in the case of exaggerated pharmacologic effect (systolic dysfunction), higher than expected plasma concentration, or excessive QTcF prolongation as described below.

If participant has a resting LVEF <50%, plasma drug concentration  $\geq$ 1000 ng/mL, or QTcF stopping criteria described below, as determined by the echocardiography central laboratory, PK analysis laboratory, or ECG core laboratory, respectively, it will be communicated to the investigator and Sponsor that a criterion for temporary discontinuation has been met. Upon receipt of this information, the study site/investigator will contact the participant by telephone and instruct the participant to discontinue study drug and to return for an onsite visit within 2 to 4 weeks (T+2 to 4 weeks). This could correspond to a scheduled or unscheduled visit. Note that to avoid potential bias the IXRS will randomly select participant(s) from the placebo arm to undergo an unscheduled follow-up visit (see also Section 6.2).

Criteria for temporary discontinuation due to QTcF prolongation are as follows and depend on QRS width as determined by the ECG core laboratory:

- If QRS is narrow ( $<120$  ms), then temporary discontinuation criteria are the smaller of: a 15% increase from baseline QTcF OR QTcF  $\geq 520$  ms
- If QRS is wide ( $\geq 120$  ms), then temporary discontinuation criteria are the smaller of: a 15% increase from baseline QTcF OR QTcF  $\geq 550$  ms

At the follow-up visit (T+2 to 4 weeks), ECG, plasma PK, and TTE will be repeated and another unscheduled visit will be planned for 2 weeks later (T+4 to 6 weeks). If LVEF  $\geq 50\%$  AND plasma drug concentration  $<1000$  ng/mL AND QTcF duration is below programmed discontinuation rules, then the study drug will be restarted at a lower dose (at T+6 weeks) for remainder of the study as follows (previous dose  $\rightarrow$  restart dose):

- Placebo  $\rightarrow$  placebo
- 2.5 mg  $\rightarrow$  placebo
- 5 mg  $\rightarrow$  2.5 mg
- 10 mg  $\rightarrow$  5 mg
- 15 mg  $\rightarrow$  10 mg

If LVEF, plasma drug concentration and/or QTcF persist out of range at the follow-up visit, then study drug will be switched permanently to placebo.

### **7.3.3           *Management of Double-blind Treatment in the Case of LVEF $\leq 30\%$ at Study Site***

Results of TTE performed by study site sonographers at each scheduled visit following randomization should be kept blinded to the investigator and other study site personnel. An exception may occur if LVEF  $\leq 30\%$  is measured at the site. Under these circumstances, the sonographer should review and re-measure the findings with at least one other non-study professional qualified in echocardiography assessment who is not the investigator (eg, echo laboratory director, other experienced sonographer or non-study cardiologist). If the result is confirmed (LVEF  $\leq 30\%$ ), then the investigator will be immediately notified and study drug will be discontinued.

Low LVEF  $\leq 30\%$ , as measured by local site, is one of the criteria for permanent treatment discontinuation ([Section 10.1.3](#)), as this finding will lead to Investigator being unblinded. It should be subsequently managed as described in [Section 10.1.4](#).

### **7.3.4           *Management of Double-blind Treatment in the Case of New or Worsening Heart Failure***

If a participant experiences heart failure related to systolic dysfunction, no further study drug should be administered and administration of therapeutic doses of a  $\beta$ -adrenergic agonist (eg, 5 to 10  $\mu$ g/kg/min dobutamine infusion) should be considered. Additional supportive measures, eg, IV volume supplementation and/or the use of arterial vasoconstrictor agents ( $\alpha$ -adrenergic agonists) should complement the use of a  $\beta$ -adrenergic agonist. Aside from this specific advice regarding the role of a  $\beta$ -adrenergic agonist, appropriate care will be determined by the treating medical personnel.

New or worsening heart failure associated with systolic dysfunction is one of the criteria for permanent treatment discontinuation ([Section 10.1.3](#)) and should be subsequently managed as described in [Section 10.1.4](#).

## **7.4               *Hepatotoxicity Stopping and Rechallenge Rules***

Participants with abnormal hepatic laboratory values (eg, alkaline phosphatase [ALP], aspartate aminotransferase [AST], alanine aminotransferase [ALT], total bilirubin [TBL], or international normalized ratio or signs/symptoms of hepatitis may meet the criteria for withholding of study medication or other protocol-required therapies. Withholding is either permanent or conditional depending on the clinical circumstances discussed below (as specified in the United States (US) Food and Drug Administration (FDA) Guidance for Industry–Drug Induced Liver Injury: Premarketing Clinical Evaluation, July 2009).

### **7.4.1           *Criteria for Permanent Withholding of Study Drug Due to Potential Hepatotoxicity***

Study drug should be discontinued permanently and the participant should be followed according to the recommendations in [Appendix 3](#) for possible drug-induced liver injury (DILI), if all the criteria below are met:

- TBL  $>2 \times$  upper limit of normal (ULN) or international normalized ratio  $>1.5$
- AND increased AST or ALT, if the baseline value was  $<\text{ULN}$  and AST or ALT elevation is  $>3 \times \text{ULN}$
- AND no other cause for the combination of laboratory abnormalities is immediately apparent. Important potential causes for abnormal AST/ALT or TBL values include, but are not limited to, the following:
  - Obstructive gall bladder or bile duct disease
  - Viral or alcoholic hepatitis (eg, hepatitis A/B/C/D/E, Epstein-Barr virus, cytomegalovirus, herpes simplex virus, varicella)
  - Hypoxic or ischemic hepatopathy or congestive hepatopathy in association with significant right sided heart failure

- Concomitant administration of other hepatotoxins, including drugs that inhibit bilirubin glucuronidation (eg, indinavir, atazanavir, irinotecan) or herbal or dietary supplements
- Heritable disorders causing impaired glucuronidation (eg, Gilbert syndrome);  $\alpha$ -1 antitrypsin deficiency
- Autoimmune hepatitis
- Nonalcoholic steatohepatitis (NASH) or other fatty liver disease

If an alternative cause for hepatotoxicity is identified or less stringent conditions developed than what is noted above, the investigator will determine whether study drug and other protocol-required therapies should be permanently or temporarily discontinued based on participant population and/or severity of the hepatotoxicity or event, as deemed appropriate for the safety of the participant.

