### **5.3 Exclusion Criteria**

A participant who meets any of the following criteria will be excluded from the study.

1. Previously participated in a clinical study with mavacamten
2. Hypersensitivity to any of the components of the mavacamten formulation
3. Participated in a clinical trial in which the participant received any investigational drug (or is currently using an investigational device) within 30 days prior to Screening, or at least 5 times the respective elimination half-life (whichever is longer)
4. Known infiltrative or storage disorder causing cardiac hypertrophy that mimics oHCM, such as Fabry disease, amyloidosis, or Noonan syndrome with LV hypertrophy
5. Has any medical condition that precludes upright exercise stress testing
6. Has a history of syncope within 6 months prior to screening or history of sustained ventricular tachyarrhythmia with exercise within 6 months prior to Screening
7. Has a history of resuscitated sudden cardiac arrest (at any time) or known history of appropriate ICD discharge/shock for life-threatening ventricular arrhythmia within 6 months prior to Screening (Note: history of anti-tachycardia pacing (ATP) within 6 months or ever is allowed)
8. Has paroxysmal, intermittent atrial fibrillation with atrial fibrillation present per the investigator's evaluation of the participant's ECG at the time of Screening
9. Has persistent or permanent atrial fibrillation not on anticoagulation for at least 4 weeks prior to Screening and/or not adequately rate controlled within 6 months of Screening (Note – patients with persistent or permanent atrial fibrillation who are anticoagulated and adequately rate-controlled are allowed)
10. Current treatment (within 14 days prior to Screening) or planned treatment during the study with disopyramide or ranolazine
11. Current treatment (within 14 days prior to Screening) or planned treatment during the study with a combination of  $\beta$ -blockers and verapamil or a combination of  $\beta$ -blockers and diltiazem
12. For individuals on  $\beta$ -blockers, verapamil, or diltiazem, any dose adjustment of that medication <14 days prior to Screening or an anticipated change in treatment regimen using these medications during the study
13. Has been successfully treated with invasive septal reduction (surgical myectomy or percutaneous ASA) within 6 months prior to Screening or plans to have either of these treatments during the study (note: individuals with myectomy or percutaneous ASA

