performed >6 months prior to Screening may be enrolled if study eligibility criteria for LVOT gradient criteria are met)

14. ICD placement or pulse generator change within 2 months prior to Screening or planned new ICD placement during the study (pulse generator changes, if needed during the study, are allowed)
15. Has QT interval with Fridericia correction (QTcF) >500 ms at Screening or any other ECG abnormality considered by the investigator to pose a risk to participant safety (eg, second-degree atrioventricular block type II)
16. Has documented obstructive coronary artery disease (>70% stenosis in one or more epicardial coronary arteries) or history of myocardial infarction
17. Has known moderate or severe (as per investigator's judgment) aortic valve stenosis at Screening
18. Has any acute or serious comorbid condition (eg, major infection or hematologic, renal, metabolic, gastrointestinal, or endocrine dysfunction) that, in the judgment of the investigator, could lead to premature termination of study participation or interfere with the measurement or interpretation of the efficacy and safety assessments in the study
19. Has pulmonary disease that limits exercise capacity or systemic arterial oxygen saturation
20. History of malignant disease within 10 years of Screening:
  - Participants who have been successfully treated for nonmetastatic cutaneous squamous cell or basal cell carcinoma or have been adequately treated for cervical carcinoma in situ or breast ductal carcinoma in situ (DCIS) can be included in the study
  - Participants with other malignancies who are cancer-free for more than 10 years before Screening can be included in the study
21. Has safety laboratory parameters (chemistry, hematology, coagulation, and urinalysis) outside normal limits (according to the central laboratory reference range) at Screening as assessed by the central laboratory; however, a participant with safety laboratory parameters outside normal limits may be included if he or she meets all of the following criteria:
  - The safety laboratory parameter outside normal limits is considered by the investigator to be clinically not significant
  - If there is an alanine aminotransferase or aspartate aminotransferase result, the value must be  $<3 \times$  the upper limit of the laboratory reference range
  - The body size-adjusted estimated glomerular filtration rate is  $\geq 30 \text{ mL/min}/1.73 \text{ m}^2$

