#### **7.4.2        *Criteria for Conditional Withholding of Study Drug Due to Potential Hepatotoxicity***

For participants who do not meet the criteria for permanent withholding of study medication outlined above, study drug should be withheld if ANY of the following criteria are met, and the participant should be evaluated for DILI:

- Elevation of either AST or ALT, regardless of baseline AST or ALT value, if:
  - $>8 \times$  ULN at any time
  - $>5 \times$  ULN and  $<8 \times$  ULN for  $\geq 2$  weeks
  - $>5 \times$  ULN and  $<8 \times$  ULN and unable to adhere to enhanced monitoring schedule
- OR: clinical signs or symptoms that are, in the opinion of the investigator, consistent with hepatitis (such as right upper quadrant pain/tenderness, fever, nausea, vomiting, jaundice, rash or eosinophilia  $>5\%$ ). If such signs or symptoms are coupled with ALT or AST elevations  $>3 \times$  ULN, study medication should be withheld
- OR: TBL  $>3 \times$  ULN at any time

OR: ALP  $>8 \times$  ULN at any time

Study drug should be withheld pending an investigation into alternative causes of DILI. If study drug is withheld, the participant should be followed according to recommendations in [Appendix 3](#) for possible DILI. Rechallenge may be considered if an alternative cause, such as acute hepatitis B infection, is discovered and the laboratory abnormalities resolve to normal or baseline (Section 7.4.3).

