#### **7.4.3        *Criteria for Rechallenge of Study Drug After Potential Hepatotoxicity***

The decision to rechallenge the participant should be discussed and unanimously agreed by the investigator and Sponsor.

If signs or symptoms recur with rechallenge, then study drug will be permanently discontinued. Participants who clearly meet the criteria for permanent discontinuation (as described in [Section 7.4.1](#)) should never be rechallenged.

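### Protocol 7.4.1 gives no AST/ALT threshold for a baseline at or above ULN, so an asymptomatic, unexplained AST/ALT of >3 to 5 × ULN with bilirubin of >2 to 3 × ULN can call for no mandatory stop or hold

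*Protocol*

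**What the plan says.** **Permanent stop (Protocol 7.4.1).** All three criteria must be met: total bilirubin (TBL) >2 × ULN or INR >1.5; a transaminase criterion; and no other immediately apparent cause. The transaminase criterion begins "AND increased AST or ALT, if the baseline value was" and is completed by baseline <ULN with elevation >3 × ULN. No line covers a baseline at or above ULN. If another cause is found, or "less stringent conditions developed than what is noted above, the investigator will determine whether study drug" should stop permanently or temporarily. The liver item in 10.1.3 refers back to 7.4.1.

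**Conditional hold (Protocol 7.4.2).** Any one criterion suffices. The transaminase criterion reads "Elevation of either AST or ALT, regardless of baseline AST or ALT value", and applies at >8 × ULN, at >5 to <8 × ULN for at least 2 weeks, or at >5 to <8 × ULN when enhanced monitoring cannot be followed. The others are clinical signs or symptoms of hepatitis, TBL >3 × ULN, and ALP >8 × ULN. There is no INR criterion. Rechallenge may be considered if an alternative cause "is discovered and the laboratory abnormalities resolve to normal or baseline".

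**Rechallenge (Protocol 7.4.3).** "The decision to rechallenge the participant should be discussed and unanimously agreed by the investigator and Sponsor". "Participants who clearly meet the criteria for permanent discontinuation" under 7.4.1 are barred from it.

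**Eligibility (Protocol 5.3).** Exclusion 21 rules out abnormal safety laboratory values, with an exception for those judged not clinically significant. On transaminases the exception says "If there is an alanine aminotransferase or aspartate aminotransferase result, the value must be" <3 × ULN.

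**Appendix 3.** Concurrent AST/ALT >3 × ULN and TBL >2 × ULN is reported as an SAE within 24 hours, on the premise that eligibility required normal liver function. Separately, any AST/ALT >3 × ULN leads to close observation.

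**SAP 10.3.1.** Potential Hy's law cases are ALT or AST >3 × ULN with TBL >2 × ULN, where the transaminase rise coincides with or precedes the bilirubin rise. There is no baseline condition.

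**The concern.** A combined rise in transaminase and bilirubin with no other explanation is the liver pattern that the protocol itself treats most severely. Whether it forces a stop depends on whether the transaminase was below ULN at baseline. Exclusion 21 lets in participants for whom it was not, and 7.4.1 has no line for them. If 7.4.2 does not catch them either, two participants with identical on-treatment values are handled differently. One must stop permanently, is barred from rechallenge and generates a 24-hour SAE report. For the other, stopping is a matter of judgement at one of about 90 sites. This is a question of participant safety and of uniform conduct. It does not touch alpha, the sample size or the primary analysis.

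**Working it through.** No figure stated in the plan bears on this point, so the check is to apply the two rules to defined cases.

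**Rules, in multiples of ULN:**
- 7.4.1 is met if (TBL >2 or INR >1.5) AND (ALT >3 with baseline ALT <1, or AST >3 with baseline AST <1) AND no other cause.
- 7.4.2 is met if AST or ALT >8, OR it is >5 to <8 for at least 2 weeks or without enhanced monitoring, OR hepatitis signs or symptoms are present, OR TBL >3, OR ALP >8.

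**Common to all cases:** no signs or symptoms, ALP normal, no other cause, enhanced monitoring followed. INR is 1.0 unless stated, and durations are under 2 weeks unless stated.

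| Case | Baseline ALT/AST | On-treatment ALT/AST | TBL | 7.4.1 | 7.4.2 |
|---|---|---|---|---|---|
| a | 1.5 / 1.5 | 4 / 4 | 2.5 | not met | not met |
| b | 1.5 / 0.8 | 4 / 4 | 2.5 | met, through AST | not met |
| c | 1.5 / 0.8 | 4 / 2.5 | 2.5 | not met | not met |
| d | 0.8 / 0.8 | 4 / 4 | 2.5 | met | not met |
| e | 1.5 / 1.5 | ALT 6 for 7 days | 2.5 | not met | not met |
| f | 1.5 / 1.5 | 4 / 4, INR 1.8 | 1.0 | not met | not met |

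Cases a and d differ only in baseline: d is a mandatory permanent stop, while a requires neither stop nor hold. A baseline of exactly 1.0 for both analytes gives the same result as a. Case b shows that one transaminase with baseline <ULN closes the gap if it passes 3 × ULN itself; case c shows that otherwise it does not.

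**Edges of the gap.** Starting from case a, 7.4.2 takes over at TBL 3.1, at ALT 9, at ALT 6 lasting 14 days, or when any hepatitis sign such as jaundice is judged present. The uncovered region is therefore TBL >2 to 3 × ULN with AST/ALT >3 to 5 × ULN, extending to <8 × ULN while the elevation has lasted under 2 weeks and monitoring is kept. Case f shows the same gap when the 7.4.1 limb is met through INR rather than bilirubin.

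**Against the SAP.** Case a has ALT 4 > 3 and TBL 2.5 > 2. Given the required time order, SAP 10.3.1 counts it as a potential Hy's law case.

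**Stop or hold as the remedy?** The rise that 4 × ULN represents depends on the baseline. Over an assumed baseline range of 1.0 to 2.9 × ULN (exclusion 21 allows <3), it runs from 4/1.0 = 4.0 times baseline, through 4/1.5 = 2.7, down to 4/2.9 = 1.4. That spread argues for a hold pending investigation rather than an automatic permanent stop.

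**The case against.** The best defence is that the case has been assigned, not overlooked. The last paragraph of 7.4.1 gives it to the investigator, and 10.1.3 requires a stop if the investigator considers continued dosing detrimental. Appendix 3 then applies whatever the baseline: retesting within 24 hours when TBL is >2 × ULN, monitoring at least twice weekly at first, INR and fractionated bilirubin, and a viral and autoimmune work-up. The abnormality must be recorded as an AE (11.1.1) and goes in as an SAE within 24 hours if it meets the general criteria (11.1.2, 11.3). Any rechallenge still needs the agreement required by 7.4.3. Exclusion 21 rules out abnormal values by default, exclusion 22 removes positive hepatitis B or C serology, and 8.1 attributes dose-limiting toxicity in animals to exaggerated pharmacology. The baseline limit also appears in both 7.4.1 and Appendix 3, which could mean that it was intended.

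All of this stands as mitigation, and it keeps the point small. None of it imposes a stop or hold, the bar on rechallenge, or the conditions that 7.4.2 sets for restarting. Intent cannot be settled from the documents, but they do anticipate raised baselines. Section 7.4.2 applies its transaminase limits whatever the baseline, and Protocol 12.4.8.3 and SAP 10.3.1 both define normalization for a baseline above ULN. Appendix 3 rests on a premise that exclusion 21 does not guarantee.

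Two stronger readings are tempting. Because Table 1 schedules on-treatment chemistry only at Weeks 6, 18 and 30, a reader might infer that such a participant could go unwatched for months; the Appendix 3 schedule rules that out. A reader might also take the 7.4.1 bullet to mean that any increase counts once baseline is not <ULN. That detaches the opening words from the condition that follows them in the same bullet, and is too strained to rely on.

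**Conclusion.** The gap is real and narrow. It needs a baseline at or above ULN for every transaminase that passes 3 × ULN, on-treatment values inside the region worked out above, no hepatitis signs or symptoms, ALP not above 8 × ULN, and no other apparent cause. There the plan leaves stopping to the investigator, while identical values from a baseline <ULN are a mandatory permanent stop.

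The case should be rare. The documents do not say how many participants have a baseline AST/ALT at or above ULN, so no number affected can be given. A reader might infer that these participants are unprotected or that their cases go unreported; the monitoring, investigator authority and general reporting rules do not support that. What is missing is a uniform mandatory action and the automatic 24-hour SAE report. This is worth correcting, at low severity. The conclusion rests on the literal wording of 7.4.1; the guidance that 7.4 cites was not available to show what it expects for a raised baseline.

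**What to change.** 1. **Section 7.4.2:** add a conditional hold for AST or ALT >3 × ULN with TBL >2 × ULN, or with INR >1.5 not explained by anticoagulant therapy, regardless of baseline AST/ALT, when no other cause is immediately apparent. Restart only under 7.4.2 and 7.4.3. This catches cases a, c, e and f.

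2. **Appendix 3:** delete the clause presuming that eligibility required normal liver function at baseline. The 24-hour SAE report then also covers these cases.

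Both limits in the first edit are needed. The anticoagulant exception avoids holds for an expected INR, since exclusion 9 notes that "patients with persistent or permanent atrial fibrillation who are anticoagulated and adequately rate-controlled are allowed". The no-other-cause limb avoids a hold in, for example, a participant with known Gilbert syndrome, a baseline TBL of 2.1 × ULN and ALT moving from 2.9 to 3.1 × ULN; 7.4.1 already lists that syndrome among the alternative causes.

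The cost is two short text changes and an occasional additional temporary hold.
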